5. TREATMENT PLAN

5.1 Treatment Regimen

Treatment will be administered on an outpatient basis. Expected toxicities and potential risks as well as dose modifications for dabrafenib, trametinib, and pembrolizumab are described in Section 6 (Expected Toxicities and Dosing Delays/Dose Modification). No investigational or commercial agents or therapies other than those described below may be administered with the intent to treat the participant's malignancy.

Response and progression will be assessed at the end of the lead-in phase, and at the start of each 3-week visit thereafter by history and physical exam or in the interim if any new symptoms arise. In addition, radiological imaging (either CT or MRI) will be obtained within 4 weeks of lead-in therapy commencement, within 1 week prior to Week 9, and at 6-week intervals (with a window of -1 week), following the commencement of pembrolizumab for 24 weeks and then extended to 12-week intervals (+2 weeks) while patients remain on the study. Response and progression will be determined based on the Response Evaluation Criteria in Solid Tumors 1.1 (RECIST 1.1). Further, if a patient does not tolerate the combination phase of combination MTT plus pembrolizumab, then MTT will be discontinued and pembrolizumab single-agent phase will begin, presuming that it is safe to treat with pembrolizumab (as outlined in Section 5.3.1).

All patients will be evaluated for anti-tumor activity of the combination. Disease control rate (DCR) at the 24-week time point after commencement of pembrolizumab (in combination with MTT) is the primary anti-tumor end-point. DCR is defined as the percentage of patients per cohort who have stable disease (SD), complete or partial response (CR, PR) without requiring restart of MTT for any reasons. Progression free survival (PFS), CR and PR rates, and overall survival (OS) will also be summarized for patients in each cohort.

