A Simon 2-stage design will be implemented for two disease cohorts, BRAF^{V600} mutant and BRAF^{V600} wild-type unresectable Stage III or Stage IV melanoma. Patients will be treated with a two-week lead-in of MTT, followed by a 6-week course of combined MTT and pembrolizumab (at dose of 200 mg IV every three weeks), followed by maintenance single-agent pembrolizumab in all patients with RECIST defined stable disease (SD), partial response (PR), and complete response (CR). *MTT only will be resumed* if patients develop symptomatic or radiographic evidence of progression. If patients do not develop evidence of progressive disease (PD), then they will continue maintenance single-agent

CONFIDENTIAL

This document is confidential. Do not disclose or use except as authorized.

pembrolizumab for up to two years; at which time treatment will be discontinued. In each cohort, patients will be accrued to first stage of the Simon design. If a pre-specified number of patients maintain SD/PR/CR off MTT but on pembrolizumab at the 24-week time point, then the second stage of the two-stage design will be opened. (Please see details in statistical section). Biopsies will be performed on all patients enrolled to the first stage of the Simon two-stage for each cohort. These will be obtained at baseline, after the two-week lead-in, and after the completion of induction therapy if feasible. An optional biopsy at the time of disease progression will also be performed.

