5.4 General Concomitant Medication and Supportive Care Guidelines

5.4.1 Acceptable Concomitant Medications

All treatments (outside of the medications or vaccinations specifically prohibited in the exclusion and in Section 5.4.2) that the investigator considers necessary for a subject's welfare may be administered at the discretion of the investigator in keeping with the community standards of medical care. All concomitant medication will be recorded on the case report form (CRF) including all prescription, over-the-counter (OTC), herbal supplements, and IV medications and fluids. If changes occur during the trial period, documentation of drug dosage, frequency, route, and date must also be included on the CRF.

All concomitant medications received within 28 days before the first dose of trial treatment and 30 days after the last dose of trial treatment should be recorded. Concomitant medications administered after 30 days after the last dose of trial treatment should only be recorded for SAEs and ECIs as defined in Section 7.

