5.4.2 Prohibited Concomitant Medications

Subjects are prohibited from receiving the following therapies during the Screening and Treatment Phase (including retreatment for post-complete response relapse) of this trial:

- Antineoplastic systemic chemotherapy or biological therapy
- Immunotherapy not specified in this protocol
- Chemotherapy not specified in this protocol
- Investigational agents other than pembrolizumab not specified in this protocol

CONFIDENTIAL

This document is confidential. Do not disclose or use except as authorized.

- Live vaccines within 30 days prior to the first dose of trial treatment and while participating in the trial. Examples of live vaccines include, but are not limited to, the following: measles, mumps, rubella, varicella/zoster, yellow fever, rabies, BCG, and typhoid vaccine.
- Systemic glucocorticoids for any purpose other than to modulate symptoms from an event of clinical interest of suspected immunologic etiology. The use of physiologic doses of corticosteroids may be approved after consultation with the Overall PI.
- Strong inhibitors/inducers of selected CYP450 isoenzymes. Dabrafenib mesylate is a substrate for CYP 3A4, 2C8, p-glycoprotein (Pgp), and breast carcinoma resistance protein (Bcrp). These enzymes and transporters are prohibited for eligibility and during the study. Because the lists of these agents are constantly changing, it is important to regularly consult a frequently-updated list such as <http://medicine.iupui.edu/clinpharm/ddis/table.aspx>; medical reference texts such as the Physicians' Desk Reference may also provide this information.
- Concomitant medications should be reviewed for the potential risk of inducing nephrotoxicity and, if so, should be modified if clinically possible (See 6.2.6)

If there is a clinical indication for one of these or other medications or vaccinations specifically prohibited during the trial, discontinuation from trial therapy or vaccination may be required. The investigator should discuss any questions regarding this with the Merck Clinical team. The final decision on any supportive therapy or vaccination rests with the subject's primary investigator. Subjects may receive other medications that the investigator deems to be medically necessary.

The Exclusion Criteria describes other medications that are prohibited in this trial.

There are no prohibited therapies during the Post-Treatment Follow-up Phase.

CONFIDENTIAL

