5.6 Duration of Follow Up

If treatment is discontinued for completion of two years of pembrolizumab, or for disease progression, or for withdrawal of consent, participants will be followed for adverse events. All adverse events encountered from time of the first dose of study treatment up until 90 days after the last dose of study treatment will be followed until one of the following occurs:

- The event resolves,
- The participating investigator assesses the event as stable,
- The participating investigator determines the event to be irreversible,
- The participant is lost to follow-up,
- The participant dies.

If the subject is not seen in clinic after the off-study visit, required Adverse Event details must be collected over the phone.

CONFIDENTIAL

This document is confidential. Do not disclose or use except as authorized.

If treatment is discontinued for a reason other than disease progression, study discontinuation, or withdrawal of consent, participants will be seen every 12 weeks (+/- 2 weeks) for imaging until progressive disease or death, whichever comes first. If there are any adverse events that have not resolved, or been assessed by the participating investigator as stable or irreversible at the time of progressive disease, the participant will be followed until the adverse events resolve, or are assessed by the participating investigator as stable or irreversible.

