11.1.4.4 Evaluation of Best Overall Response

The best overall response is the best response recorded from the start of the treatment until disease progression/recurrence (taking as reference for progressive disease the smallest measurements recorded since the treatment started). The patient's best response assignment will depend on the

achievement of both measurement and confirmation criteria.

For Participants with Measurable Disease (i.e., Target Disease)

Target Lesions	Non-Target Lesions	New Lesions	Overall Response	Best Overall Response when Confirmation is Required*
CR	CR	No	CR	≥4 wks Confirmation**
CR	Non-CR/Non-PD	No	PR	≥4 wks Confirmation**
CR	Not evaluated	No	PR	
PR	Non-CR/Non-PD/not evaluated	No	PR	
SD	Non-CR/Non-PD/not evaluated	No	SD	Documented at least once ≥4 wks from baseline**
PD	Any	Yes or No	PD	no prior SD, PR or CR
Any	PD***	Yes or No	PD	
Any	Any	Yes	PD	

* See RECIST 1.1 manuscript for further details on what is evidence of a new lesion.
 
** Only for non-randomized trials with response as primary endpoint.
 
*** In exceptional circumstances, unequivocal progression in non-target lesions may be accepted as disease progression.
 
Note: Participants with a global deterioration of health status requiring discontinuation of treatment without objective evidence of disease progression at that time should be reported as “symptomatic deterioration.” Every effort should be made to document the objective progression even after discontinuation of treatment.
				

For Participants with Non-Measurable Disease (i.e., Non-Target Disease)

Non-Target Lesions	New Lesions	Overall Response
CR	No	CR
Non-CR/non-PD	No	Non-CR/non-PD*
Not all evaluated	No	not evaluated
Unequivocal PD	Yes or No	PD
Any	Yes	PD

* ‘Non-CR/non-PD’ is preferred over ‘stable disease’ for non-target disease since SD is increasingly used as an endpoint for assessment of efficacy in some trials so to assign this category when no lesions can be measured is not advised
		

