11.1.6 Progression-Free Survival

Overall Survival: Overall Survival (OS) is defined as the time from randomization (or registration) to death due to any cause, or censored at date last known alive.

Progression-Free Survival: Progression-Free Survival (PFS) is defined as the time from randomization (or registration) to the earlier of progression or death due to any cause. Participants alive without disease progression are censored at date of last disease evaluation.

Time to Progression: Time to Progression (TTP) is defined as the time from randomization (or registration) to progression, or censored at date of last disease evaluation for those without progression reported.

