13.1 Study Design/Endpoints

Primary Endpoint: The rate of clinical benefit (CBR), defined as the proportion of patients who have CR/PR/SD at the week-24 scan while remaining off MAPK-targeted therapy (MTT) after induction. To be evaluable for the primary endpoint, patients must receive at least one dose of pembrolizumab, any patient who is unevaluable for response will be classified as a non-responder.

Secondary Endpoints:

13.1.1 Overall Survival (OS): The time between the first dose of targeted therapy and death from any cause. For patients who are lost to follow-up or who have no documentation of death at the time of final analysis, follow-up will be censored at the date of last assessment of vital status.

13.1.2 Safety and tolerability: Safety and toxicity will be monitored throughout the study. An early, comprehensive safety review will be conducted at the end of the first-stage of the Simon two-stage design to review the data for unexpected severe toxicities due to the drug combination.

13.1.3 Describe temporal changes in the tumor microenvironment as a function of therapy.

Design: For each disease cohort, the Simon two-stage design is based on a type-I error rate of 0.1, at least 85% power, and a total sample size of 25 subjects. A complete safety assessment is planned to coincide with the review of clinical benefit at the end of the first stage.

Within cohort, the null hypothesis of a true CBR of 0.50 will be tested against a one-

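### A patient who stops protocol therapy without progression and starts another anticancer drug can still count as clinical benefit and as a responder, and the drug need not be recorded after 30 days

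*Combined protocol and SAP*

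**What the plan says.** - **Treatment phase.** Section 5.1 bars other agents given to treat the melanoma: "No investigational or commercial agents or therapies other than those described below may be administered". The list in Section 5.4.2 covers screening and treatment.
- **After treatment.** Section 5.4.2 ends with "There are no prohibited therapies during the Post-Treatment Follow-up Phase".
- **Imaging.** For a patient who stops for a reason other than progression, study discontinuation or withdrawal of consent, Section 5.6 says "participants will be seen every 12 weeks (+/- 2 weeks) for imaging until progressive disease or death, whichever comes first". A new anticancer drug does not end this.
- **Recording.** Section 5.4.1: "Concomitant medications administered after 30 days after the last dose of trial treatment should only be recorded for SAEs and ECIs".
- **Primary endpoint.** Section 13.1 gives the CBR as "defined as the proportion of patients who have CR/PR/SD at the week-24 scan while remaining off MAPK-targeted therapy (MTT) after induction". The synopsis and Section 1.2 likewise disqualify only for resumed targeted therapy, as does the disease control rate in Section 5.1.
- **Opening stage 2.** Section 5.1 asks that a set number of patients "maintain SD/PR/CR off MTT but on pembrolizumab at the 24-week time point". The synopsis says the same, and Section 1.1 is similar but gives no time point.
- **ORR.** The synopsis counts patients with a best response of CR or PR. Section 11.1.4.4: "The best overall response is the best response recorded from the start of the treatment until disease progression/recurrence".
- **PFS.** Section 11.1.6: "Participants alive without disease progression are censored at date of last disease evaluation".

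**The concern.** Leaving off-protocol care unrestricted is ordinary and is not the fault. The fault is that the endpoint text does not say what happens when a patient who has not progressed takes up a different systemic anticancer drug. Sections 13.3, 13.4 and 13.7.2 do not say either. Read literally, later scans still count, and disease control under the other drug is attributed to the regimen.

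For CBR and ORR this can only help the regimen, and a single-arm trial has no control group to offset it. The CBR count decides whether a cohort passes 9 of 14 and then 16 of 25. The recording rule adds to the problem, because the analysts may not be told that a new drug was started.

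**Working it through.** **Step 1. Follow one patient through the text.** Suppose pembrolizumab is stopped for toxicity before the week-24 scan, without progression, and another systemic drug that is not MTT is started.

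| Question | Rule as written | Result |
|---|---|---|
| Is the drug allowed? | 5.4.2 | Yes, in follow-up |
| Is imaging continued? | 5.6 | Yes, every 12 weeks |
| Is the patient in the CBR denominator? | 13.1: one dose of the combination, whatever the reason for stopping | Yes |
| Does CR, PR or SD at the week-24 scan count? | 13.1: only MTT disqualifies | Yes |
| Does a later CR or PR count for ORR? | 11.1.4.4 | Yes, until progression |
| Must the drug be recorded? | 5.4.1 | Only within 30 days of the last dose, or for an SAE or ECI |

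Pembrolizumab starts in week 3, so the 24-week scan falls at about week 27. Thirty days is 4.3 weeks. A patient whose last dose is before about week 22 can start a drug ahead of that scan with no instruction to record it. Section 5.4.4 asks for concurrent drugs to be captured because of interactions, which does not lengthen the window.

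The protocol foresees the event. Section 5.5.1.4 allows retreatment after a complete response only if no other cancer treatment has been given since pembrolizumab. No endpoint uses that information.

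**Step 2. Reproduce the design.** Inputs from Section 13.1: n1 = 14, stop at 8 or fewer; n = 25, reject at 16 or more; null 0.50, alternative 0.75; type I error limit 0.10.

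- P(stop) = Σ(x = 0 to 8) Bin(x; 14, p)
- P(reject) = Σ(x = 9 to 14) Bin(x; 14, p) × P(Bin(11, p) ≥ 16 − x)

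At p = 0.50, P(stop) = 0.788 (stated 0.79). P(reject) = 0.0335 + 0.0305 + 0.0161 + 0.0049 + 0.0008 + 0.0001 = 0.086 before rounding of the terms. At p = 0.75, P(reject) = 0.862 (stated 86%). The stated figures are right, and the room below 0.10 is 0.014.

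**Step 3. Credit one patient.** Assume that one patient always counts as benefit through other therapy and that the other 24 follow the null of 0.50.

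- Stage-1 patient: Σ(x = 8 to 13) Bin(x; 13, 0.5) × P(Bin(11, 0.5) ≥ 15 − x) = **0.122**
- Stage-2 patient: Σ(x = 9 to 14) Bin(x; 14, 0.5) × P(Bin(10, 0.5) ≥ 15 − x) = **0.109**
- One in each stage: 0.153

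**Step 4. Express it as a rate.** Let s be the share of patients who stop without progression and start other therapy, and f the share of the would-be failures among them who are then credited. At a null of 0.50, half would have succeeded anyway, so the effective CBR is 0.50 + 0.5 × s × f. The documents give neither s nor f; these values are assumptions.

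| s | f | Effective CBR | Type I error |
|---|---|---|---|
| 5% | 0.25 | 0.506 | 0.096 |
| 5% | 0.50 | 0.5125 | 0.106 |
| 10% | 0.25 | 0.5125 | 0.106 |
| 10% | 0.50 | 0.525 | 0.130 |
| 15% | 0.25 | 0.519 | 0.118 |
| 15% | 0.50 | 0.5375 | 0.157 |

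An effective null CBR of 0.51 already gives 0.102.

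**The case against.** **Few patients may be affected.** Those who progress first are already PFS events with best response closed. Those who cannot tolerate the combination drop MTT and move to single-agent pembrolizumab if that is safe (Section 5.1), so they remain in the treatment phase, where other agents are barred. A scan at the 24-week point is not assured for a patient on a 12-weekly (±2 weeks) schedule, and a patient unevaluable for response is a non-responder (Section 13.1). All of this stands. It limits the size of the bias but does not close the gap.

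**A large figure is tempting.** Section 2.2.1.2 reports that 26.7% (4 patients) stopped for treatment-related events in the cited phase 1 study of the triplet. A reader might assume that a quarter to a half of such patients switch, that all would otherwise fail and that 60% are then controlled. That gives a CBR of 0.54 to 0.58 and type I error of 0.163 to 0.274. The documents do not support it:

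- Median time on therapy in that study was 115 days, against six weeks of triplet here. The 26.7% is an outer bound for leaving all protocol therapy.
- At a null of 0.50, about half of the switchers would have succeeded anyway. That alone gives 0.50 + 0.267 × (0.25 or 0.50) × 0.5 × 0.60 = 0.52 to 0.54, and type I error of 0.120 to 0.163.
- The 60% is a response rate for a different combination (Section 2.1), not for patients who have just stopped anti-PD1 for toxicity.

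If 10% leave all therapy and a quarter of them switch, with the same 60% and the halving, the CBR is 0.5075 and type I error 0.098, below the limit.

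**Stage 1 is partly guarded.** If the on-pembrolizumab wording governs the interim count, only stage 2 is exposed. CBRs of 0.52 and 0.54 there, with 0.50 in stage 1, give 0.096 and 0.106. The stage-1 figure of 0.122 needs the Section 13.1 definition at the interim. The guard is real, but it is absent from the endpoint definition and does not reach ORR.

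**The data may be obtainable.** A reader might infer that the error could never be found later. That goes too far: the endpoint itself requires MTT status to be known, patients are seen every 12 weeks, and the CRFs are not in the documents. What is missing is an instruction to record the therapy.

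**PFS is a choice.** Following patients to progression whatever they take next is a recognised treatment-policy approach, and a progression after switching counts against the regimen. No one-way bias can be claimed for PFS.

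**Conclusion.** The gap is real for CBR and ORR. As written, both can credit the regimen with another drug's effect, in the regimen's favour. The stage-2 opening text and the Section 13.1 definition also set different conditions for what is meant to be the same count.

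The size cannot be determined, because the documents give no rate of switching before progression. What can be said is that the margin is thin: type I error goes from 0.086 to 0.109 (stage-2 patient) or 0.122 (stage-1 patient) if one null patient in 25 is always credited. This assumes that the credit is certain, that the other 24 patients are at 0.50 and, for the stage-1 figure, that Section 13.1 governs the interim. With lower switching the error can stay below 0.10.

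The design figures are correct and the trial is not invalidated. This is an inexpensive repair to the endpoint text and data collection. For PFS, the plan need only state its rule.

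**What to change.** 1. **Section 13.1.** Count a patient who starts non-protocol systemic anticancer therapy before the week-24 scan as not having clinical benefit. Use this one definition at the interim and final counts, and reconcile it with the stage-2 wording in the synopsis and Sections 1.1 and 5.1.
2. **Section 11.1.4.4.** For best response, use only assessments made before the first non-protocol systemic anticancer therapy.
3. **Section 5.4.1.** Record every subsequent systemic anticancer therapy, with its start date, for as long as the patient is imaged.
4. **Section 11.1.6.** State whether PFS follows patients regardless of new therapy or censors at the last assessment before it, and run the other as a sensitivity analysis.

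**Cost.** A few sentences and one CRF item. No visits, scans or patients are added and no patient's care is restricted. Under rule 1, no credit can come from other therapy, so type I error at a true null of 0.50 under that definition stays at 0.086.

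CBR and ORR may be slightly lower. If the planned 0.75 was meant under the present definition and 5% of patients switch irrespective of outcome, the counted CBR becomes 0.75 × 0.95 = 0.7125 and power 0.758. Section 13.1 should therefore say that 0.50 and 0.75 refer to the revised definition.

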5.4.3 Concomitant Medications to be used with caution

The following therapies are to be used with caution during the Screening and Treatment Phase (including retreatment for post-complete response relapse) of this trial:

- Mild or moderate inhibitors/inducers of CYP 3A4, 2C8, Pgp, and Bcrp should be used with caution as dabrafenib serum concentrations may be altered. Because the lists of these agents are constantly changing, it is important to regularly consult a frequently-updated list such as <http://medicine.iupui.edu/clinpharm/ddis/table.aspx>; medical reference texts such as the Physicians' Desk Reference may also provide this information.
- Dabrafenib may induce CYP 3A4, 2B6, and possibly 2C8/9 and 2C19. Use concomitant medications that are substrates of these isoenzymes with caution as there may be loss of efficacy. Substitute with other medications that are not affected if possible.
- Because there is a low potential for interaction of trametinib with other concomitantly administered drugs through the cytochrome P450 system, the Principal Investigator should be alerted if the patient is taking any agent known to affect or with the potential to affect selected CYP450 isoenzymes.

5.4.4 Alerting the Principal Investigator about specific agents and capturing the concurrent use of all drugs, over-the-counter medications, or alternative therapies in the case report form

- Because there is a potential for interaction of dabrafenib with other concomitantly administered drugs through the cytochrome P450 system, the case report form must capture the concurrent use of all other drugs, over-the-counter medications, or alternative therapies. The Principal Investigator must be alerted if the patient is taking any agent known to affect or with the potential to affect selected CYP450 isoenzymes.
- Because there is a low potential for interaction of trametinib with other concomitantly administered drugs through the cytochrome P450 system, the case report form must capture the concurrent use of all other drugs, over-the-counter medications, or alternative therapies. The Principal Investigator should be alerted if the patient is taking any agent known to affect or with the potential to affect selected CYP450 isoenzymes.

CONFIDENTIAL

This document is confidential. Do not disclose or use except as authorized.

